Patients with end-stage liver disease (ESLD) have poor physical fitness and muscle wasting (sarcopenia). Both conditions have been associated with elevated mortality before and after liver transplantation (LT). Limited data have shown that exercise benefits patients with chronic liver disease/cirrhosis, however, there are no studies with ESLD patients potentially eligible for LT. Effectively improving physical fitness and sarcopenia in ESLD should positively impact clinical outcomes before/after LT. The primary aim of this study is to improve both physical fitness and sarcopenia in ESLD patients through a 12-week physical training program. Secondary aims will focus on changes in anthropometrics, body composition, quality of life, and metabolic profile. This is a randomized clinical trial including 50 patients, with half allocated to the active group (physical training program) and half to standard of care. Physical training program will consist on achieving $\geq 10,000$ steps/day with an increase of ≥ 4000 above the baseline, facilitated by the feedback from daily step counts and behavioral modification therapy (favoring change towards a more active lifestyle). All participants will have to wear a pedometer bracelet (Fitbit) throughout duration of study (reads blinded to controls), and will receive a daily essential amino acid (EAA) supplement containing approximately 2.25 g of L-leucine along with nutritional consultation. Cardiorespiratory exercise test (CRET), 6-minute walk test (6MWT), and abdominal CT scan will be performed in all participants before and after the period of study to assess for physical fitness and sarcopenia. Anthropometrics, bioelectrical impedance, whole-body DEXA scan, sickness impact profile questionnaire, and the metabolic profile will be obtained at baseline and after completion of the study as well. Blood EAA levels, myostatin, and insulin-related growth factor-1 will be determined at baseline, and at week 12 of study. Durability of changes 6 months post-LT will be assessed as well, when applicable.

INTRODUCTION

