The study will occur over a total of 14 weeks, although duration of the intervention will consist of 12 weeks. The first two weeks will serve the purpose of identifying the baseline physical activity of each participant. During the second week all baseline studies/determinations will be completed, with randomization occurring by the end of week 2. Allocation will be stratified by presence or absence of refractory ascites.

Follow up visits for behavioral therapy will occur every 2 weeks for the first 8 weeks, and then on a 4-weekly basis (only active group). Nutritional consultation will occur every 2 to 4 weeks throughout the study (both active and control group). During each visit, the EAA supplement jar will be inspected for percent emptiness (in analogy to a pill count) in order to quantify adherence. Bi-weekly phone calls will be made to all subjects to enhance adherence to recommendations. Standard of care investigations (blood chemistries, hematology and coagulation, liver function tests, etc.) will be ordered according to the needs of the patient and the criteria of the investigator or responsible clinician. Clinical status and complications from portal hypertension, particularly variceal bleeding and HE, will be systematically investigated on each visit.

Research Tests - Variables to Measure

Prior to randomization each subject will be scheduled to undergo all baseline investigations, as follows (see Research Calendar below):

Cardiorespiratory stress test (CRET) and anaerobic threshold (Week -1, Day 1)

CRET will be performed early in the morning on a fasting state, following the maximal incremental cycle ergometry protocol from our Pulmonary Physiology Laboratory, and in agreement with the American Thoracic Society.(38) Briefly, test consists on having the patient on a cycle ergometer performing a progressively increasing work rate until reaching: volitional exhaustion, or termination by the medical monitor. The Borg Rating of Perceived Exertion Scale will be used to help titrate intensity of work rate (aiming for a level of 13 to 17). Gas exchange measurement for

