The 6MWT will be performed in agreement with the recommendations of the American Thoracic Society.(39) In brief, the test will be done indoors, along a long and flat enclosed corridor, aiming for as many laps (100 ft per half-lap) as possible, while patient is wearing a pulse oximeter. The investigator applying the test will use a stopwatch and write down heart rate and oxygenation, at baseline, and every minute until reaching a total of six minutes. The Modified Borg Scale will be used to rate shortness of breath and fatigue before and after the test. This test will be repeated after completion of the study period (12 weeks), and 6 months after LT.

Sarcopenia (abdomen CT-scan) (Week -1, Day 3)

A noncontrasted abdominal CT-scan will be used to measure the cross-sectional area of skeletal muscle at the level of the third lumbar vertebrae (L3). Images will be analyzed with SliceOmatic 4.3 (Tomovision, Montreal, Canada) measuring the cross-sectional area of skeletal muscle at this level (*i.e. psoas, paraspinals, quadratus lumborum, transversus abdominis, rectus abdominis, and internal and external obliques*). Muscle areas will be analyzed by an operator trained in musculoskeletal anatomy with tissue-specific Hounsfield unit thresholds (-29 to +150).(16) The L3 skeletal muscle area will be normalized to stature by the division of the muscle area by the height squared. Sarcopenia will be defined as a reduction in the L3 area of muscle mass $\leq 52.4 \text{ cm}^2/\text{m}^2$ in males and $\leq 38.5 \text{ cm}^2/\text{m}^2$ in females. This test will be repeated after completion of the study period (12 weeks), and 6 months after LT.

Nutritional consultation, anthropometrics, and body composition (Week -2, Day 3)

A dietitian or designated investigator will evaluate anthropometrics (weight, height, waist circumference), bioelectrical impedance, and whole-body dual energy X-ray absorptiometry scan (DXA). Bioelectrical impedance will be performed according to the manufacturer's recommendations: after overnight fasting, with subject in supine position with arms and legs abducted from the body, and source and sensor electrodes placed on the dorsum of both hand and foot on the right side of the body, respectively. After obtaining resistance (R), reactance (Xc)

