Unlike CRET, in the 6MWT each patient determines the intensity of their exercise according to symptoms and cardiorespiratory fitness. The 6MWT is thus considered a very safe procedure, and it has been performed (without electrocardiogram monitoring) in thousands of older persons and thousands of patients with heart failure or cardiomyopathy without serious adverse events. Although patients with cardiopulmonary disease may be at increased risk for arrhythmias or cardiovascular collapse during testing, it is very unlikely for a complication to be witnessed given the selection criteria followed during LT evaluation (as above).

The risks associated with placement of an IV catheter and blood collection from a vein are minor bleeding, bruising, infection (a small risk any time the skin is broken), or needing more than one attempt to locate veins.

Both CT and DXA scans are associated with exposure to small amounts of ionizing radiation. The abdominal CT-scan will be restricted to a simple phase (non-contrasted) in order to limit radiation exposure, and thus it should not exceed 10 mSv. Since the initial CT-scan is performed as part

Title: A physical activity program in end-stage liver disease
PI: [name]

of the LT evaluation (standard of care), the study will derive in radiation exposure of approximately 20 mSv. This is a very low radiation exposure that might be associated with a low additional increase in lifetime risk for cancer (1 in 1000 to 10,000). In the case of DXA, exposure per whole-body scan is similar to daily background natural radiation exposure (0.01 mSv).

The electrical current used in bioelectrical impedance is very small and thus unlikely to stimulate electrically excitable tissues, particularly cardiac and nervous tissues. Moreover, there are no reports of untoward effects among thousands of individuals in whom bioelectrical impedance analysis has been performed. Actually, the currents employed are very small and below the threshold of perception.

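### Does calling the baseline abdominal CT standard of care contradict its listing as a Week -1 research test, or undo the 20 mSv exposure figure?

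*Combined protocol and SAP*

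**What the plan says.** **When and how the baseline scan is done.** The opening summary says that an "abdominal CT scan will be performed in all participants before and after the period of study". Follow Up sets the window: "During the second week all baseline studies/determinations will be completed, with randomization occurring by the end of week 2". Research Tests - Variables to Measure adds "Prior to randomization each subject will be scheduled to undergo all baseline investigations, as follows", and the CT is listed there under the heading "Sarcopenia (abdomen CT-scan) (Week -1, Day 3". That subsection specifies a non-contrast scan at L3, repeated at 12 weeks and 6 months after transplant.

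**How the scan is classed for risk.** Risks and Benefits says the abdominal CT is "restricted to a simple phase (non-contrasted) in order to limit radiation exposure, and thus it should not exceed 10 mSv". The next sentence, split by a page break, reads "Since the initial CT-scan is performed as part" and then "of the LT evaluation (standard of care), the study will derive in radiation exposure of approximately 20 mSv".

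**Who has the last scan.** The opening summary makes the post-transplant assessment conditional: "Durability of changes 6 months post-LT will be assessed as well, when applicable".

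**The concern.** Read separately, the sections seem to describe two baseline scans. One is a research procedure on a fixed day in the second run-in week. The other belongs to the transplant evaluation, carries no stated date and is left out of study exposure. No sentence says they are the same scan, and none says when an existing evaluation scan may stand in for the Week -1 scan.

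Two things could be at stake.

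- **Endpoint.** L3 muscle area serves one of the two primary aims. The hypothesis in Specific Aims, that only the active arm will gain muscle, leans on within-arm change, which Statistical analysis tests with paired methods. An older scan, or one taken with contrast, would blur that change.
- **Disclosure.** If the Week -1 scan is an extra study scan, the exposure total omits it. A single figure also cannot fit both transplanted and non-transplanted participants.

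**Working it through.** **1. Reproduce the stated figure.** Inputs from Risks and Benefits: at most 10 mSv per CT and 0.01 mSv per DXA. Inputs from the CT subsection: scans at baseline, week 12 and 6 months after transplant.

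Study CT exposure = (CT scans attributed to the study) x 10 mSv.

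On the risk section's own premise the baseline is routine. The study scans are then week 12 and post-transplant: 2 x 10 = 20 mSv, which is the stated figure. Three DXA scans add 3 x 0.01 = 0.03 mSv, which is negligible.

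**2. Vary the two unknowns.** CT only, at the ceiling:

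| Baseline scan | Not transplanted | Transplanted |
|---|---|---|
| Routine, not counted | 1 x 10 = 10 mSv | 2 x 10 = 20 mSv |
| Separate study scan | 2 x 10 = 20 mSv | 3 x 10 = 30 mSv |

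The stated 20 mSv is exact in two cells, too high in one and too low in one. The low cell needs a separate study baseline scan and a post-transplant scan in the same participant.

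**3. Timing as scheduled.** Take Week -2 as run-in days 1-7 and Week -1 as days 8-14.

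- Week -1, Day 3 is run-in day 7 + 3 = 10.
- Randomisation is by day 14, so the scan precedes it by at most 14 - 10 = 4 days.
- The 12-week intervention is 84 days, so scan to week 12 is at most 4 + 84 = 88 days.
- The pre-randomisation share is at most 4/88 = 4.5%.

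A scan done no later than run-in day 1 would precede the slot by at least 10 - 1 = 9 days. That scan is hypothetical: no section describes or permits one as the baseline.

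The Study Calendar is not used here, because its column alignment is uncertain in the text available.

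**4. Set the passages side by side.** Follow Up and the CT subsection answer when and how: second run-in week, before randomisation, non-contrast. Risks and Benefits answers under which heading the scan is done, namely the transplant evaluation. It also restricts the abdominal CT to a non-contrast phase, in the sentence just before it mentions the initial scan. The two statements answer different questions. A non-contrast evaluation CT done in Week -1 satisfies both.

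**5. Effect on the comparison.** Suppose some baseline scans were older. Their age would be fixed before allocation, so it could not favour either arm in expectation. It would add time and noise to the paired within-arm change. The documents give no variability or rate of change for muscle area, so no size can be put on that.

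**The case for a change.** The strongest opposing case starts from recruitment. Approach draws participants from hepatology clinics as well as from transplant referrals. Its standard-of-care note covers only eligibility criteria, and the L3 CT is not one of them. A clinic patient may therefore have no evaluation CT in Week -1. The Week -1 scan would then be a study scan, and if that patient were later transplanted the total would be up to 30 mSv, not 20. The same section ties a lifetime cancer-risk statement to the 20 mSv figure, and a linking sentence would cost little.

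Part of this stands. The risk section does not say that its total includes a scan only transplanted participants have, and it does not identify the evaluation CT with the Week -1 scan.

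The rest is weaker. Every participant must be a potential transplant candidate, so an evaluation CT is plausible for clinic patients too. The documents give no count of people without one, and the number may be zero. A clinic patient who has a study baseline but no transplant is at 20 mSv, as stated. The consent pages are not in the material available, so conditional exposure wording cannot be presumed absent.

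A formal rule limiting when a routine scan may serve is also not costless. It could require a further research CT of up to 10 mSv for some participants, in return for a gain that cannot be quantified.

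**Conclusion.** The concern does not call for a change to the plan. The baseline of the muscle measure is already fixed by Follow Up and the CT subsection as a non-contrast, pre-randomisation scan in Week -1. The risk section's label does not override that. The 20 mSv figure is arithmetically right on its own premise. Across all readings the ceiling runs from 10 to 30 mSv, and the figure is exceeded only where a separate study baseline and a post-transplant scan coincide. No between-arm bias arises in expectation, and no effect size on the endpoint can be derived.

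This rests on three assumptions: that staff follow the scheduled window and non-contrast technique, that the 10 mSv ceiling holds per scan, and that post-transplant imaging is confined to those transplanted. What remains is missing detail that staff can settle when booking the scan. Stating it would leave the scheduled baseline and the analysis as they are.

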38. ATS/ACCP Statement on cardiopulmonary exercise testing. *American journal of respiratory and critical care medicine*. 2003;167(2):211-77.
39. ATS statement: guidelines for the six-minute walk test. *American journal of respiratory and critical care medicine*. 2002;166(1):111-7.

Title: A physical activity program in end-stage liver disease

PI: [name]

STUDY CALENDAR

	Basal	Wk -2	Wk -1	Wk 0	Wk 2	Wk 4	Wk 6	Wk 8	Wk 12	Post-LT
Sign consent	✓									
CRET			✓						✓	✓
Anaerobic threshold				✓					✓	✓
6MWT				✓					✓	✓
NH3 & Lactate thresholds				✓					✓	
CT scan				✓					✓	✓
SIP		✓							✓	
Bioimpedance & DXA			✓						✓	✓
Nutritional consultation					✓	✓	✓	✓		
Pill count						✓	✓	✓	✓	✓
Anthropometry		✓						✓	✓	✓
Pedometer count		✓			✓	✓	✓	✓	✓	
Heart rate count		✓			✓	✓	✓	✓	✓	
Cognitive Therapy						✓	✓	✓		
Metabolic profile	✓								✓	✓
Myostatin & IGF-1				✓					✓	
Essential amino acids				✓					✓	

Cognitive therapy will be provided only to the active group.

IGF-1: insulin-related growth factor 1
